**(d) Procedures:**

Study visit

For prospectively enrolled controls and pilot study participants, following participant consent, study staff/providers will collect sociodemographic, clinical, and mobility questionnaires from patients directly and from records, and a blood sample to test viral load. Study staff/providers will have access to clinical records during the study visit and can query patients and clinical staff regarding key clinical variables if data are missing from records. Sociodemographic data and mobility measures will be collected directly from the participant. Data will be collected directly into REDCap, a secure platform for building and managing datasets which has an off-line data collection option enabling use in settings where internet access may be limited.

For participants who are reached and consented outside of the clinic via tracing, data will be collected in a location convenient to the patient.

Samples collected for viral load testing will immediately be stored in a cooler bag and will be tested for HIV RNA levels with Cephied's GeneXpert® technology, Xpert HIV-1 Viral Load on the same day.

Intervention

Our enhanced virologic monitoring intervention includes 3 components: 1) More frequent viral load collection than standard of care, 2) Rapid return of viral load results, 3) Enhanced viral load counselling, including about low-level viremia. These are detailed below.

### 1) More frequent viral load collection

Our research assistants will be trained in phlebotomy. All participants who have not had a viral load collected within the prior 80 days will have a blood sample collected at baseline for viral load testing. Those who enroll in the first 3 months of the pilot study period will be eligible for a follow-up visit within the 6-month pilot study period, and will have viral load assessed again at the 3-month follow up visit.

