## **3. DESIGN AND METHODOLOGY**

The study will be conducted within MoH clinics, in Kisumu County, Kenya. Kisumu County is one of the regions of Kenya most affected by the HIV epidemic: in 2015, adult HIV prevalence (age 15-49) was 20% and the rate of perinatal transmission was 20%.

In a 6-month pilot study, we will evaluate the implementation and potential impact of enhanced virologic monitoring for pregnant and postpartum women living with HIV to reduce the risk of viremia and loss from care. Prior to the pilot study, we will sample 2 control groups: 1) 125 women will be prospectively enrolled at the pilot study sites (as part of the CAPS mobility sub-study), and 2) 150-320 women will be randomly selected from de-identified electronic medical records.

**(a) Study sites:** 2-4 clinics will be selected for the pilot study.

**(b) Study populations:** All women seeking care at these sites who are on ART **and**, either in their 3rd trimester of pregnancy, in the maternity ward for delivery, or within the first 6 months postpartum are eligible. Our rationale for this time range is: (1) Late pregnancy and delivery are critical periods for prevention of mother to child transmission. (2) 0-6 months postpartum is a period highly susceptible to disengagement from care among women living with HIV.

**(c) Sampling:** For prospectively enrolled controls and pilot study participants, to ensure adequate representation from each facility and to avoid seasonal differences by site, we will conduct recruitment at each site simultaneously, visiting each site within any given week in which recruitment is done, to the best of our ability. We will invite all women attending clinic on days of recruitment at each site, and will trace all women late for visits that were due on those recruitment days. Controls selected from records only will be randomly sampled from eligible women with viral loads scheduled for collection in the 6 months prior to the pilot study.

Recruitment.

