### HIV care outcomes.

The viral loads collected as part of the intervention will guide the counselling that is provided during the study. Study outcome viral loads will be routine care viral loads that are collected (1) within the 6 months following the control participants enrollment (and only) study visit, for prospectively enrolled controls, (2) within the 6 months prior to the pilot study for controls

retrieved from electronic records, and (3) within the 6 months following the pilot participants last study visit. The study team will work together with the clinical teams to ensure these viral load outcomes are measured and recorded according to national guidelines. Viremia will be defined as any detectable levels of HIV RNA. Suboptimal care engagement will be defined as late for a clinic visit by 30 days or more.

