#### **4. DATA MANAGEMENT**

Analyses of implementation outcomes. Analyses will summarize acceptability and feasibility survey results, summaries of adoption, as well as the clinical and sociodemographic characteristics of the women seen at the clinic during the pilot study, using descriptive statistics.

Evaluating the potential impact on maternal viremia. The frequency of viremia in the year preceding the pilot to the frequency among women seeking care during the pilot will be

compared with logistic regression, adjusted for baseline differences in clinical and demographic characteristics.

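### Prospective controls also receive a study viral load, so the viremia comparison should be shown separately for prospective and record controls

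*Combined protocol and SAP*

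**What the plan says.** Section 3(d) lists three intervention components, the first being "1) More frequent viral load collection than standard of care". The other two are rapid return of results and enhanced counselling.

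The study visit is shared by two groups: "For prospectively enrolled controls and pilot study participants, following participant consent, study staff/providers will collect" questionnaires "from patients directly and from records, and a blood sample to test viral load". The sample is tested the same day. For a prospective control this result is not the outcome. Under HIV care outcomes, her outcome is a routine viral load taken "within the 6 months following the control participants enrollment (and only) study visit, for prospectively enrolled controls".

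For the pilot, component 1 sets two rules. On the baseline draw: "All participants who have not had a viral load collected within the prior 80 days will have a blood sample collected at baseline". On the repeat draw at 3 months: "Those who enroll in the first 3 months of the pilot study period will be eligible for a follow-up visit".

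Section 3 also defines a second control group: "150-320 women will be randomly selected from de-identified electronic medical records". These women have no study visit.

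Section 4 gives the analysis in one sentence: "The frequency of viremia in the year preceding the pilot to the frequency among women seeking care during the pilot will be" compared by logistic regression, adjusted for baseline clinical and demographic differences. It mentions no split by control source or by enrolment period.

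**The concern.** The two control groups differ in their exposure to component 1. Record controls had routine care only. Prospective controls had routine care plus one study viral load before the outcome was measured. The Detailed Description argues that viral load monitoring can in itself strengthen adherence. On that rationale, the study test could lower later viremia among prospective controls as well.

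The pilot group is also mixed. Early enrollees can have two study viral loads and late enrollees at most one. A late enrollee drawn at baseline has the same testing schedule as a prospective control: one visit, one study test, then a routine outcome test within 6 months.

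A single contrast averages over all of this. If the study test has an effect of its own, the pooled difference would tend to be smaller than the difference from women without one. A reader planning the next study could take a weak pooled result as little potential impact without seeing that some controls had received part of the package.

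**Working it through.** The plan gives no power calculation, effect size or expected viremia rate, so there is no figure to reproduce. The check is a count of scheduled study viral loads before the outcome test.

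| Group | Women | Study viral loads | Source |
|---|---|---|---|
| Record controls | 150 to 320 | 0 | Section 3 |
| Prospective controls | 125 | 1 | Section 3(d), Study visit; HIV care outcomes |
| Pilot, enrolled months 4-6 | not stated | at most 1 | Section 3(d), component 1 |
| Pilot, enrolled months 1-3 | not stated | at most 2 | Section 3(d), component 1 |

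The entries say at most because of the 80-day rule. That rule stands under the intervention heading, while the study visit text has no such exception, so whether it reaches controls is unclear. On any reading, a woman enrolling in months 4-6 is scheduled for no more study tests than a prospective control who was drawn.

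**Share of controls with a study test.** 125/(125 + 150) = 125/275 = 45%. With 320 record controls, 125/445 = 28%.

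**Contrast in testing.** Let q be the share of the 275 pilot women who enrol in months 4-6. The documents do not give q. I assume 1/2, with a range of 1/3 to 2/3 (about 138 women, range 92 to 183). If every pilot woman is drawn at baseline, the pilot mean is 2(1 - q) + q = 2 - q. The mean difference in study viral loads is then:

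- against record controls, 2 - q = 1.50 (1.67 to 1.33);
- against prospective controls, 1 - q = 0.50 (0.67 to 0.33);
- against pooled controls, 2 - q - 125/275 = 1.05 (1.21 to 0.88), or 2 - q - 125/445 = 1.22 (1.39 to 1.05) with 320 record controls.

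These are differences in exposure. They say nothing about how much viremia changes per test.

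**Precision cost of separating the sources.** For a difference in proportions with equal underlying risks, the standard error is proportional to sqrt(1/n1 + 1/n2). Relative to the pooled comparison:

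- 150 record controls: sqrt[(1/275 + 1/150)/(1/275 + 1/275)] = 1.19;
- 125 prospective controls: sqrt[(1/275 + 1/125)/(1/275 + 1/275)] = 1.26;
- with 320 record controls in the plan, against them: sqrt[(1/275 + 1/320)/(1/275 + 1/445)] = 1.07;
- in the same case, against 125 prospective controls: sqrt[(1/275 + 1/125)/(1/275 + 1/445)] = 1.41.

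Restricting the pilot group to early enrollees costs more. If half enrol early (137.5 women, an assumption), the ratio against 150 record controls is sqrt[(1/137.5 + 1/150)/(2/275)] = 1.38.

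**The case against.** The strongest reply is that a blood draw is not the intervention. The plan says that intervention viral loads guide counselling, and it describes return of results and counselling only as intervention components. It never says that prospective controls receive their results. A test whose result does not reach the woman may do little for adherence. This stands, and it rules out the stronger claim that a reader might infer, namely that controls were given the intervention and a real effect will be masked. The documents support only a conditional statement.

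Component 1 is defined against standard of care, not against prospective controls. A late enrollee drawn at baseline still has one study test plus components 2 and 3. That also stands: late enrollees are not untreated, and the contrast with record controls is intact. It does not remove the difference between the two control sources.

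A reader might infer from the 80-day rule that some pilot women are monitored less than controls. The documents do not support this, because an excused woman has by definition had a recent viral load.

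Pooling is the natural reading of section 4 but is not stated, and the outcome windows are set out by control group. Section 4's silence does not prove that the sources will be combined.

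Finally, section 3 already says that the pre-post comparison is not causal and explores potential impact only. This lowers the stakes. It is a general caution, however, and does not tell the reader that the two control groups had different exposure. Table 1 records for each enrolled participant whether monitoring was on schedule, which overlaps with part of the fix but does not show the number of study tests by comparison group.

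**Conclusion.** The point holds in a limited form. Between 28% and 45% of controls receive one study viral load before their outcome test, the rest receive none, and pilot women receive at most one or two depending on when they enrol. Those counts come from the text. The average contrast in testing against prospective controls is about a third of that against record controls (0.50 versus 1.50) if half the pilot women enrol late and all are drawn at baseline.

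Whether this attenuates the viremia estimate depends on a study test having an effect of its own, most plausibly when the result reaches the woman, and on the sources being pooled. The documents settle neither, so the amount of attenuation is unknown and I put no figure on it. Components 2 and 3 still separate the groups, and no decision rule rests on the comparison. This is a cheap improvement to consider, not a flaw that undermines the pilot.

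**What to change.** In section 4:

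1. Report the adjusted viremia comparison against record controls and against prospective controls, beside the pooled estimate.
2. Tabulate study viral loads per woman (0, 1, 2) by group, keeping tests not due apart from tests missed.
3. As a supplementary analysis, repeat the comparisons for pilot women enrolled in months 1-3. Define them by enrolment date, not by tests received, so that the group is not selected on attendance. Adjust for time since delivery at the outcome test, because the outcome window opens after the last study visit and so comes later for these women.
4. Describe the prospective-control comparison as mainly one of rapid return and counselling, plus a second draw for early enrollees.

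One sentence in section 3(d) on whether and how controls' results are returned, and on whether the 80-day rule applies to controls, would help interpretation.

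The cost is text and a few more model fits, with no extra visits or draws. The separate intervals will be wider by the ratios worked out above, and wider again for early enrollees alone. Keeping the pooled estimate beside them means that no precision is lost from the report as a whole.

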### 2) Rapid return of viral load results:

Mentor mothers will be trained to return viral load results to patients with scripted messaging according to viral load level (undetectable, low-level viremia (50-1000), high viral load (>1000)). Patients will be offered a choice of the mode of delivery, including text, phone, or in-person. Detectable viral loads will not be delivered by text, and women with high viral loads may be asked to return to the clinic for in-person counselling.

### 3) Enhanced viral load counselling

Mentor mothers will reinforce adherence with all patients with undetectable levels via scripted messaging to reward and encourage healthy behavior. For those with any detectable levels, mentor mothers will be trained to provide targeted counseling about low-level and higher viral loads. Women who report significant psychosocial barriers will be referred to a social worker.

## Study Measures.

### Baseline characteristics.

To assess objective 3 and the objectives of the sub-study, we will collect information about women's baseline characteristics (individual and social) that we believe may be confounders of the associations we plan to estimate (ie., the impact of enhanced virologic monitoring on subsequent viremia; the impact of mobility on viremia and retention in care). These baseline characteristics will include the following, and the surveys are included as an appendix to this protocol:

- Sociodemographic and health information (e.g., marital status, education, mobility)
- Clinical records data abstraction (pregnancy history, HIV history – from records)
- Household food insecurity scale (HFIAS)
- Perceived stress scale (to measure psychosocial stress)
- Edinburgh depression scale (to measure perinatal depression)

If, during the depression questionnaire, a study participant expresses an intent to harm themselves or scores 11 or higher, they will be referred to social services (e.g., social worker, psychiatrist, other mental health provider) for further assessment on the same day. Because this questionnaire will be collected on REDCap, the score will be automatically generated once the form is completed. The social service staff member is not part of the study team. The study will cover the cost of an initial consultation for patients who would benefit from further assessment up to ~2000 KShs or ~\$20 USD. If further care is recommended, the participant will be responsible for those costs. We note these potential costs in the informed consent form.

### HIV care outcomes.

The viral loads collected as part of the intervention will guide the counselling that is provided during the study. Study outcome viral loads will be routine care viral loads that are collected (1) within the 6 months following the control participants enrollment (and only) study visit, for prospectively enrolled controls, (2) within the 6 months prior to the pilot study for controls

retrieved from electronic records, and (3) within the 6 months following the pilot participants last study visit. The study team will work together with the clinical teams to ensure these viral load outcomes are measured and recorded according to national guidelines. Viremia will be defined as any detectable levels of HIV RNA. Suboptimal care engagement will be defined as late for a clinic visit by 30 days or more.

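### The outcome window for prospectively enrolled controls does not stop at pilot launch or at a woman's own pilot enrolment, so a viral load drawn after pilot exposure can count as a control outcome (minor)

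*Combined protocol and SAP*

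**What the plan says.** The section on HIV care outcomes (within section 3) takes outcomes from routine-care viral loads and gives each group its own window:

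- Prospective controls: "1) within the 6 months following the control participants enrollment (and only) study visit, for prospectively enrolled controls".
- Pilot participants: "within the 6 months following the pilot participants last study visit".
- Controls taken from records: the half-year before the pilot, so this window is closed by launch.

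Section 4 describes the comparison differently, as "The frequency of viremia in the year preceding the pilot to the frequency among women seeking care during the pilot", and the Brief Summary calls the comparator historical.

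On who the controls are, section 3 says that "125 women will be prospectively enrolled at the pilot study sites (as part of the CAPS mobility sub-study". The Detailed Description places their enrolment before the pilot. Neither place gives dates or a minimum gap before launch.

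On pilot recruitment, the Sampling paragraph says "We will invite all women attending clinic on days of recruitment at each site". Eligibility runs from the third trimester to six months after delivery, about 9 months in all. Earlier participation as a control is not listed as an exclusion.

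Two further rules bear on exposure. The control visit already includes a viral load ("and a blood sample to test viral load"). In the pilot, "All participants who have not had a viral load collected within the prior 80 days will have a blood sample collected at baseline", and "Those who enroll in the first 3 months of the pilot study period will be eligible for a follow-up visit".

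**The concern.** A control seen less than 6 months before launch has a window that runs into the pilot. She attends a pilot site, may still be eligible, and would be invited if she came on a recruitment day. If she joins and her next routine viral load falls inside her control window, the plan counts it as a control outcome although she has had the intervention. If it also falls after her last pilot visit, it meets the pilot group's definition as well, and no rule says where it belongs.

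If the intervention works, exposed controls pull the comparison toward no difference. Separately, such a window reaches beyond the period that section 4 gives for the comparator, so the analysis text and the outcome definition no longer describe the same control outcomes. Controls taken from records are not affected.

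**Working it through.** The plan states no viremia rate, effect size or enrolment date, so there is no figure of its own to reproduce. The size has to be shown as a range.

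**From the documents:** 125 prospective controls; 150 records controls (section 3 allows up to 320); 275 pilot participants; a 6-month pilot; a 6-month control window; the 80-day rule; a second visit only for women enrolling in the first 3 months.

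**Assumed:** viremia of 20% in controls and 12% in the pilot group; control visits spread evenly over the T months before launch; time from delivery at the control visit, e, uniform from -3 to 6 months; time from control visit to routine viral load, v, uniform over 0 to 6 months; every still-eligible control joins. Let t be the time from control visit to launch and u the time from launch to joining. She can join if e + t + u ≤ 6. Exposure is counted only through joining.

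**Step 1: outcomes drawn after launch.** P(v > t) is 0.75, 0.50 and 0.25 for T = 3, 6 and 12. Multiplied by 125, this is about 94, 63 and 31 viral loads. Drawn after launch does not mean drawn after exposure.

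**Step 2: upper limit.** Every eligible control joins on day 1 (u = 0) and is exposed at once. For T = 6 the share is (1/6)∫₀⁶ [(9−t)/9][(6−t)/6] dt = 126/324 = 0.389. For T = 3 and 12 it is 0.639 and 0.194.

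**Step 3: spread joining with the 80-day rule.** Now u is uniform over 0 to 6 months. A woman joining within 80 days (2.63 months) of her control visit has no baseline pilot viral load. Her first pilot result comes 3 months later if u ≤ 3, and otherwise never. The affected share f, by simulation, is 0.124, 0.073 and 0.036, or about 16, 9 and 5 women.

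**Step 4: effect on the estimate.** Observed difference = 8 × (1 − f × 125/275).

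| | T = 3 | T = 6 | T = 12 |
|---|---|---|---|
| Spread joining, 80-day rule | 7.55 | 7.74 | 7.87 |
| Day-1 joining, 80-day rule | 7.04 | 7.27 | 7.63 |
| Day-1 joining, exposed at once (upper limit) | 5.68 | 6.59 | 7.29 |

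With 445 controls the first row becomes 7.72, 7.84 and 7.92. Halving uptake halves each loss. The plan does not say whether a joiner without a new viral load is counselled on an older result. If joining alone counts as exposure, spread joining affects about 25, 14 and 7 outcomes. The loss is then 8 × 25/275 = 0.73, 8 × 14/275 = 0.41 or 8 × 7/275 = 0.20 points.

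**Step 5: scale.** The standard error is √(0.20×0.80/275 + 0.12×0.88/275) = √0.000966 = 0.031, or 3.1 points. The first-row losses of 0.45 to 0.13 points are about 15% to 4% of one standard error.

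**Step 6: viral loads in both windows.** With spread joining, 125 × P(joins and v falls after the last pilot visit) is about 3.5 at T = 6 and 1.7 at T = 12. With day-1 joining it is about 14 and 7.

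**The case against.** The strongest reply is that none of this need happen. If control enrolment closed 6 months or more before launch, every control window ends before the pilot and nothing is misclassified. These controls belong to a mobility sub-study, and its own documents, which are not in view, may give dates or a rule on re-enrolment. This stands, and it means the point concerns what the text permits.

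Second, section 4 is loosely worded for both groups. It describes pilot women by care sought during the pilot, although their outcomes are taken after the last study visit. It reads as a summary, and an analyst would normally follow the specific definitions under HIV care outcomes. This also stands. A reader might infer that the two sections flatly contradict each other, but they diverge for prospective controls only if some were seen less than 6 months before launch.

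Third, the plan says the pre-post comparison is not causal. That limits the stakes. The caveat cites temporal or other factors, however, and does not settle which viral loads are control outcomes.

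Finally, the largest figures need every eligible control to join on the first day, whereas the plan describes recruitment on recruitment days and expects some women to enrol after the first 3 months. They are limits, not forecasts.

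**Conclusion.** The point holds as a minor one. As written, the rule can count a post-exposure viral load as a control outcome, and can place a few viral loads in both groups, if some control visits fall within 6 months of launch and some of those women join the pilot. The documents neither state nor exclude either condition.

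Under the more realistic spread-joining case the loss is about 0.1 to 0.45 of 8 points, even with full uptake. That is small beside a standard error of 3.1. The result rests on the assumed viremia rates, even timing and full uptake.

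A reader might infer that the control group is contaminated, or that most prospective-control outcomes are compromised. The documents do not support this: they give no enrolment dates and no sign that controls joined, and the 64% figure (T = 3) is an upper limit that also ignores the 80-day rule.

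**What to change.** If control enrolment closed at least 6 months before launch, state the date; that settles the point. Otherwise:

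- (a) Under HIV care outcomes, count a prospective control's viral load only if it is drawn within 6 months of her control visit and before her own pilot enrolment. Check this through the existing list linking study and clinic IDs (section 5). No viral load then counts in both groups.
- (b) In section 4, refer to those outcome definitions for all groups, in place of both period phrases in the comparison sentence.
- (c) Add a sensitivity analysis limited to prospective-control viral loads drawn before launch. This does not select on joining.

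The cost is wording, one date check per prospective control, and some lost outcomes, shown here for T = 3, 6 and 12:

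| Outcomes removed | T = 3 | T = 6 | T = 12 |
|---|---|---|---|
| (a), spread joining | 25 | 14 | 7 |
| (a), day-1 joining | 80 | 49 | 24 |
| (c) | 94 | 63 | 31 |

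The cut-off in (c) makes the standard error about 15%, 9% or 4% larger (ratios 1.145, 1.085 and 1.038, from reducing 275 controls by the numbers above).

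Rule (a) may also select slightly on engagement in care, because it drops outcomes only from women who join. If joiners' own viremia were 5 points below that of other controls, 8 points would show as about 8.2 (spread) to 8.4 (day 1) at T = 6. This is why (c) should accompany it.

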#### **Detailed Description:**

The investigators will examine the use of more frequent virologic monitoring with enhanced communication around low-level viremia as a strategy to identify and support pregnant and postpartum women at risk of virologic failure. Virologic monitoring itself can reinforce adherence in stable patients, and more frequent monitoring can detect potential adherence challenges early. Notably, low-level viremia is a strong predictor of subsequent virologic failure, and the lowest level associated with perinatal transmission is not known.

The pilot study will run for 6 months at 4 Ministry of Health facilities in Kisumu County, Kenya; 275 participants will be enrolled. Prior to the pilot study, 125 controls will be enrolled prospectively, and 150 controls will be abstracted from records from the prior year.

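### Records controls are selected by the date a viral load was due but scored by the date it was drawn, within one window closing at pilot start, so their viremia may be understated

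*Combined protocol and SAP*

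**What the plan says.** Section 3, under Sampling, has records controls "randomly sampled from eligible women with viral loads scheduled for collection in the 6 months prior to the pilot study". That frame is set by due date.

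The HIV care outcomes section sets the outcome by draw date: "Study outcome viral loads will be routine care viral loads that are collected" in a window that differs by group.

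- Records controls: "within the 6 months prior to the pilot study for controls" taken from electronic records.
- Prospective controls: "within the 6 months following the control participants enrollment (and only) study visit".
- Pilot participants: "within the 6 months following the pilot participants last study visit".

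For records controls the due-date frame and the draw-date window are therefore the same 6 months, and both end at pilot start. The plan gives no grace period and no rule for a sampled woman without a result in the window.

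Two provisions support complete outcomes. The team will "work together with the clinical teams to ensure these viral load outcomes are measured and recorded", and at recruitment of the prospective groups it "will trace all women late for visits that were due on those recruitment days". Neither can change when a records control was drawn in the past.

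The length of the control period also varies. The Detailed Description says "150 controls will be abstracted from records from the prior year", and the Data Management section compares viremia with that in the year before the pilot. Sampling and HIV care outcomes both use 6 months.

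**The concern.** The due date and the draw date differ only for women tested late. Requiring both to fall in one closed window removes some of those women at the right edge and admits none at the left. Take pilot start as day 0 and the window as the 182 days before it:

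- Due day -150, drawn day -148: counted.
- Due day -20, drawn 30 days late on day +10: in the frame, but the result falls outside the window.
- Due day -190, drawn 40 days late on day -150: the result lies in the window, but this test does not bring her into the frame.

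The other two groups' windows run forward from a study visit whatever the due date. A routine test overdue at the visit and drawn afterwards can count there, offsetting late draws lost at the far end.

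The protocol treats being 30 days or more late for a visit as suboptimal engagement, and its Introduction attributes most viremia to poor adherence. If late-drawn women are more often viremic, the records controls look better suppressed than they were, and a real benefit of the intervention could be partly hidden. These women are 150 to 320 of the 275 to 445 controls (125 + 150 to 125 + 320). The planned covariate-adjusted logistic regression has no stated way to handle results that were never counted.

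**Working it through.** The plan states no viremia rate, share of late draws, length of delay, power or effect size, so there is no figure of its own to reproduce. The check asks how far the rule alone moves the observed rate.

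**Inputs from the documents.** Due-date frame (Sampling); draw-date window (HIV care outcomes); both 6 months, taken as 182 days; 150 to 320 records controls; 30 days as the protocol's lateness threshold.

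**Assumptions.** Due dates are spread evenly over the window. Each woman has one routine test. A share q of draws is late by a mean of L days. Viremia is p1 in late draws and p0 in the rest. There is no intervention effect.

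**Formulas.**

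- Share of late draws lost past launch: f = L/182. This is 30/182 = 16%, 60/182 = 33% and 90/182 = 49%.
- Full rate: (1-q)·p0 + q·p1.
- Rate under the plan: [(1-q)·p0 + q·(1-f)·p1] / (1 - q·f).
- Records controls without an outcome: q·f.
- Null odds ratio: odds at the full rate divided by odds under the plan. This takes the enrolled groups to show the full rate.

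**Mild case** (q = 10%, L = 30, p1 = 30%, p0 = 15%)
- Full: 0.135 + 0.030 = 16.5%.
- Plan: (0.135 + 0.1 × 0.835 × 0.30)/(1 - 0.0165) = 16.3%.
- Shortfall 0.2 points; odds ratio 1.02; about 2 of 150 (5 of 320) without an outcome.

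**Middle case** (q = 20%, L = 60, p1 = 40%, p0 = 15%)
- Full: 0.12 + 0.08 = 20.0%.
- Plan: (0.12 + 0.2 × 0.670 × 0.40)/(1 - 0.0659) = 18.6%.
- Shortfall 1.4 points; odds ratio about 1.09; about 10 of 150 (21 of 320) without an outcome.

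**Severe case** (q = 30%, L = 90, p1 = 50%, p0 = 15%)
- Full: 0.105 + 0.150 = 25.5%.
- Plan: (0.105 + 0.3 × 0.505 × 0.50)/(1 - 0.148) = 21.2%.
- Shortfall 4.3 points; odds ratio 1.27; about 22 of 150 (47 of 320) without an outcome.

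**Where the bias vanishes or reverses.** With p1 = p0 the two rates are equal, so the bias is zero. With on-time viremia 20%, late viremia half that, 20% of draws late and delays of 1 to 3 months, the plan overstates control viremia by 0.3 to 0.9 points.

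**Source of the loss.** In simulation, counting any draw made in the window whatever its due date returned the full rate. The loss therefore comes from requiring both dates in one window.

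**Pooling.** If the records controls are pooled with the 125 prospective controls, the middle-case shortfall becomes 1.4 × 150/275 = 0.8 points, or 1.4 × 320/445 = 1.0 point.

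**The case against.** The strongest objection concerns the comparison groups. The Procedures section takes blood for a viral load at the study visit. The intervention text limits the pilot baseline draw to women not tested in the prior 80 days, so overdue women would be tested then. The plan does not say whether an overdue routine test is still drawn later or is replaced by the study draw. If it is replaced, the enrolled windows also lose late draws at the far edge with nothing entering at the near edge. The loss is then the same L/182 and the null odds ratio is 1.00. This stands: the difference between groups depends on a point the documents leave open.

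Second, the outcome is any routine viral load drawn in the window, not one particular test. A woman with another draw in the window keeps an outcome, so L/182 is an upper bound on the loss of late-tested women. This also stands.

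Third, the effect is small against the study's precision. At an assumed 20% viremia, 275 pilot women against 150 records controls give a 95% margin on the odds ratio of exp(1.96 × √(1/44 + 1/24)) = a factor of 1.64, or 1.50 with 320 controls. The protocol also disclaims a causal reading of the pre-post comparison. This limits the consequence. It does not justify the mismatch, because that disclaimer concerns temporal and other factors rather than an avoidable outcome rule.

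A reader might infer that all late draws drop out, or that control viremia is shown to be understated. The documents support neither. Only draws that cross launch are lost, so about 84% are kept at a 30-day delay and 67% at 60 days. No section gives viremia by lateness, and the adherence statement in the Introduction is only indirect support.

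**Conclusion.** The mismatch is in the text and no other section repairs it. Followed as written, the plan leaves some sampled records controls without a countable outcome for a reason unrelated to whether they were eventually tested.

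The direction is conditional. Viremia in the records controls may be understated, by about 0.2 to 4 points under the assumed rates, with a null odds ratio of about 1.02 to 1.27. This rests on late draws being more often viremic, one test per woman, evenly spread due dates and, for the odds ratio, overdue routine tests in enrolled women still being drawn and counted. If the direction is as assumed, the bias works against the intervention. The 125 prospective controls are outside the problem. The point is modest in size but worth correcting before the records are queried, because the correction is cheap and the pilot is meant to inform later research.

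**What to change.** **Preferred.** Sample records controls from eligible women whose routine viral load was due in the 6-month window or already overdue when it opened, and count any routine viral load drawn in that window. Late draws leaving at launch are then balanced by late draws entering at the start. In simulation this restores 20.0% in the middle case and 25.5% in the severe case, with no shift in calendar time. It assumes a stable pattern of lateness. It balances the missing results rather than removing them: in the middle case q·f/(1 + q·f) = 0.066/1.066 = 6% of sampled women still have no outcome, so the sample size should allow for this.

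**Alternative.** Place due dates early enough in the prior year that a fixed 6-month collection period after each due date ends before launch. These controls are older in calendar time, which adds to the temporal confounding the protocol already acknowledges. Shortening the collection period to 3 months does not help if delays are long. With delays uniform on 30 to 150 days, 59/120 = 49% of late draws exceed 91 days, and the severe case gives (0.105 + 0.3 × 0.508 × 0.50)/(1 - 0.1475) = 21.3% against 25.5%, no real gain over the current rule.

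**In either case:**
- State whether a study-visit draw replaces an overdue routine test in the enrolled groups.
- Report the number without an outcome in each group.
- Reconcile the 6-month period in Sampling and HIV care outcomes with the one-year period in the Detailed Description and Data Management.

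**Cost.** A few sentences of protocol text and a changed date filter in the records query. No tests are added. The alternative also costs calendar-time closeness.
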